#### **2.4.5 Analyses of immunogenicity variables**

An anti-drug antibody positive participant is defined as a participant with at least one treatment-induced or treatment-boosted ADA-positive sample at any time.

Summaries of ADA data will be provided for participants treated with efpeglenatide only. All summaries related to kinetics of ADA response (ADA status and magnitude, ADA attributes, participant status, ADA incidence) will be descriptive; no statistical significance tests will be performed on ADA data. The incidence of ADA status (positive/negative/inconclusive) will be summarized by visit, treatment, and individual titer for the ADA population. Incidence of treatment induced and treatment-boosted (treatment emergent) ADA during on-study period will be summarized by treatment. Incidence of participants with ADA cross-reactivity to endogenous GLP-1 (positive/negative), and to endogenous glucagon (positive/negative) will be summarized by visit and treatment. Incidence of participants with ADA directed against PEG linker, HMC001 moiety and exendin-4 moiety (positive/negative), will be summarized by visit and treatment. Analysis will be conducted as appropriate to assess the relationship with hypersensitivity reactions.

Incidence of participants with neutralizing antibodies against efpeglenatide and against endogenous GLP-1 and Glucagon will be summarized by visit and treatment.

ADA data from unscheduled visits (due to SAE for example) will not be included in summary and will be presented only in ADA values listing.

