### ***Analysis of all TEAEs***

The following TEAE summaries will be generated for the safety population.

- Overview of TEAEs, summarizing number (%) of patients with any
  - TEAE
  - Serious TEAE
  - TEAE leading to permanent treatment discontinuation
  - TEAE leading to death
  - Serious TEAE leading to permanent treatment discontinuation
- All TEAEs by primary SOC and PT, sorted by the internationally agreed SOC order and by decreasing incidence of PTs within each SOC. This sorting order will be applied to all other tables by SOC and PT, unless otherwise specified.
- All TEAEs related to IMP by primary SOC, and PT
- All TEAEs by maximal severity, presented by primary SOC and PT
- Common TEAEs (e.g., PTs  $\geq 2\%$  in any treatment group) by primary SOC, and PT
- Common TEAEs (e.g., PTs  $\geq 5\%$  in any treatment group) by primary SOC and PT and by intrinsic factors: age group ( $<50$ ,  $\geq 50$  to  $<65$ ,  $\geq 65$  to  $<75$ ,  $\geq 75$  years), sex (Male, Female), race (White, Black or African American, Asian, Other), and any pertinent subgroups as appropriate.
- All TEAEs by primary SOC and PT and by subgroup BMI ( $<30$ ,  $\geq 30$  to  $<40$ ,  $\geq 40$  kg/m^2)
- All TEAE by primary SOC and PT and by anti-efpeglenatide antibody status (positive, negative)
- Kaplan-Meier plot, for the time to first onset of the following PTs: nausea, vomiting and diarrhea

- The frequency of TEAEs over time will be provided for nausea, vomiting and diarrhea, using 3-month time intervals, i.e., [0-3] month, (3-6] month, (6-9] month, (9-12] month, etc. In each time interval, the numerator in the calculation of percentages will be the number of participants with at least 1 TEAE occurring in this time interval. Two types of analyses will be included:
  - (1) only the first event will be counted for each participant and all recurrent events will not be included, and the denominator for the calculation of percentages will be the number of participants at risk at the beginning of the time interval who did not experience a first event in the preceding intervals;
  - (2) the recurrent events in subsequent intervals will be counted once for each participant in the numerator of the corresponding interval, and the denominator for the calculation of percentages will be the number of participants at risk at the beginning of the time interval.

A histogram of the frequency over time (by 3-month intervals) will also be presented as appropriate.

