#### **2.5.5 Unscheduled visits**

Unscheduled visit measurements of laboratory data, vital signs, and ECG will not be included in the by-visit summaries, but will be used for computation of baseline, last on-treatment value, and PCSAs.

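### SAP 2.4.5 defines ADA positivity by a positive sample at any time, but its last sentence keeps unscheduled ADA samples out of summary, so treatment-emergent ADA incidence may be understated

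*SAP*

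**What the plan says.** SAP 2.4.5 opens with the participant-level rule: "An anti-drug antibody positive participant is defined as a participant with at least one treatment-induced or treatment-boosted ADA-positive sample at any time". It then lists descriptive summaries. Most are by visit and treatment (ADA status, cross-reactivity, antibodies to parts of the molecule, neutralizing antibodies). One is not: "Incidence of treatment induced and treatment-boosted (treatment emergent) ADA during on-study period will be summarized by treatment". On clinical consequences it says only: "Analysis will be conducted as appropriate to assess the relationship with hypersensitivity reactions".

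The section closes with the rule at issue: "ADA data from unscheduled visits (due to SAE for example) will not be included in summary". Such data go to the listing of ADA values and nowhere else.

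Three other places bear on this:

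- SAP 2.2.5 admits a participant to the ADA population on one valid post-baseline sample, without requiring it to be scheduled.
- SAP 2.3.5.1 plans a table of treatment-emergent adverse events (TEAEs) by antibody status.
- SAP 2.5.5 takes unscheduled laboratory, vital sign and ECG measurements out of the by-visit summaries, but they "will be used for computation of baseline, last on-treatment value, and PCSAs".

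**The concern.** The first and last sentences of SAP 2.4.5 give different answers for the same person. Someone positive only on an unscheduled sample is ADA positive by definition, yet contributes nothing positive to the summaries. Programmers would have to choose between the two rules, and the literal choice lowers the reported incidence.

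The samples left out are not a random subset. The SAP's own example is a sample taken because of an SAE. If participant status followed the same exclusion, a participant with a reaction could also appear in the ADA-negative column of a table of events by ADA status.

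**Working it through.** The plan gives no figure to reproduce, so the check is a comparison of the rules.

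1. **Who counts as positive.** SAP 2.4.5 requires one treatment-induced or treatment-boosted positive sample. SAP 2.1.5 defines both kinds by what happens at any point after the first administration. Neither section restricts this to scheduled visits.
2. **Who is in the denominator.** SAP 2.2.5 needs one valid post-baseline sample, scheduled or not.
3. **What is excluded.** All unscheduled ADA data, which "will not be included in summary and will be presented only in ADA values listing".
4. **How far the exclusion reaches.** For a by-visit table it is natural, since an unscheduled sample has no visit to sit under. The on-study treatment-emergent incidence is not a by-visit table. SAP 2.4.5 also names participant status and ADA incidence among its descriptive summaries. Nothing in the closing sentence exempts them.
5. **How the SAP words a by-visit limit when it means one.** SAP 2.5.5 states it outright and keeps unscheduled values for potentially clinically significant abnormalities (PCSAs), which are any-time counts per participant. SAP 2.4.5 has no such limit.

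**One participant followed through.** Negative at baseline, non-positive on every scheduled sample, positive on one unscheduled sample. Step 1: positive. Step 2: in the denominator. Step 3: the positive result is left out. The participant is therefore in the denominator and not in the numerator.

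**Effect on incidence.** Let N be the ADA population, S the participants positive on at least one scheduled sample, and U those positive only on an unscheduled sample.

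- By the definition: (S + U)/N.
- By the literal exclusion: S/N.
- Difference: U/N, which is zero or positive. Dropping post-baseline samples can lower the count of positives and cannot raise it.

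**Scale.** The documents do not give U, the number of unscheduled ADA samples, or an ADA rate. What can be stated is the weight of one participant. With 1:1:1 allocation of about 4000, the two efpeglenatide arms hold 2/3 × 4000 ≈ 2667. If all were in the ADA population, each such participant would move the pooled incidence by 1/2667 ≈ 0.04 percentage points.

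**When U can exceed zero.** Protocol 1.3 schedules ADA samples at Weeks 0, 12, 24 and 48, then every 48 weeks, at the premature end-of-treatment visit, and at closeout for those still on study drug. After Week 48 a short-lived response can fall inside a 48-week gap. For participants who stop study drug permanently, the premature end-of-treatment sample narrows that gap.

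**The case against.** The best defence is that the two sentences can be read together. One defines status and the other limits what is tabulated, and most tables in the section are by visit, so the authors may have meant by-visit tables only. That may well be the intent. The text does not say so, and the on-study incidence is a summary to which the literal rule applies.

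A second defence is that scheduled-only sampling gives more even ascertainment. Participants with events may be sampled more often and so have more chances to test positive, which can create an association between events and ADA. This stands for the comparisons of events by ADA status and shapes the fix. It does not remove the conflict with the any-time definition.

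Four stronger inferences are tempting, and the documents do not support them:

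- *That positives are excluded from the hypersensitivity analysis and the TEAE-by-ADA table.* The SAP does not state which samples either one uses. Their exclusion can be inferred from the listing-only wording, but it is not written.
- *That a sample drawn at a reaction is usually the only one near the event.* Protocol 1.3 and 8.8.1 require no ADA sample at an SAE or reaction. The only reaction-linked samples are at 4 and 6 months after treatment, for participants ADA positive at end of study who had a severe injection site or hypersensitivity reaction.
- *That a number of misclassified participants can be given.* Assuming that 0.5% to 1% of 2667 have an SAE-triggered sample gives 13 to 27 participants. That rate is not in the documents, and the result counts participants sampled. Misclassification also needs a positive result then and no positive scheduled sample.
- *That a safety signal is hidden.* Severe allergic and severe injection site reactions are events requiring specific monitoring and are summarized whatever the ADA status. SAEs are listed individually, and the unscheduled ADA values remain in their listing.

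**Conclusion.** The point holds for participant-level ADA status and on-study treatment-emergent incidence. The closing sentence of SAP 2.4.5, followed as written, conflicts with the definition that opens the section. Any resulting error in incidence is downward, by U/N. U is unknown and may be small or zero, since it requires an unscheduled positive in someone with no positive scheduled sample, including the premature end-of-treatment sample.

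For the hypersensitivity analysis and the TEAE-by-ADA table, the finding is only that the sample set is unspecified. ADA is an exploratory endpoint summarized without tests, so the primary analysis and the control of type I error are unaffected. The correction is worth making because the two rules cannot both be programmed as written and the change is cheap.

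**What to change.** Replace the closing sentence of SAP 2.4.5 with:

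*Unscheduled ADA samples are excluded from by-visit summaries only; they count toward participant-level ADA status and on-study treatment-induced/treatment-boosted incidence.*

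Report, by treatment group, the number of participants positive only on an unscheduled sample, so that the contribution of extra sampling is visible.

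State the sample set for the TEAE-by-ADA table and the hypersensitivity analysis: use the all-sample status, and add a version based on scheduled samples only, because participants with events may be sampled more often. If the two versions agree, uneven sampling does not drive the result; if they differ, the reader can see by how much.

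The cost is one SAP sentence, one count and one extra descriptive table. No new samples are needed, and the ADA rule then matches SAP 2.5.5.

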#### **2.4.6 Analyses of pharmacokinetic variables**

Not applicable.

#### **2.4.7 Analyses of quality of life/health economics variables**

Not applicable.

## 2.5 DATA HANDLING CONVENTIONS

### 2.5.1 General conventions

The following formulas will be used for computation of parameters.

#### *Demographic formulas*

The participant's duration of diabetes (years) is calculated using the date of informed consent and the date of diabetes diagnosis.

If date of diabetes diagnosis is a complete date, then the duration of diabetes is (date of informed consent - date of diabetes diagnosis + 1) / 365.25. If date of diabetes diagnosis is a partial date:

- a) year and month are not missing, but day is missing, then day = 01
- b) year is not missing, but month and date are both missing, then month = January and day = 01.

#### *Renal function formulas*

The estimated GFR (mL/min/1.73 m^2) will be calculated using the 4 variable MDRD formula:

Standard unit: eGFR (mL/min/1.73 m^2) = 175 x [Serum Creatinine (μmol/L)/88.4]-1.154  
x Age (year)-0.203 x 1.212 (if Black) x 0.742 (if female)

Conventional unit: eGFR (mL/min/1.73 m^2) = 175 x Serum Creatinine (mg/dL)-1.154  
x Age (year)-0.203 x 1.212 (if Black) x 0.742 (if Female)

#### *Laboratory safety variables*

For data below the lower limit of quantification (LLOQ) / limit of linearity, half of the lower limit value (i.e., LLOQ/2) will be used for quantitative analyses. For data above the upper limit of quantification (ULOQ) / limit of linearity, the upper limit value plus a unit value based on the digit of the variable following the sponsor's standard convention (i.e., ULOQ+0.01 if the digit is 2 for the parameter) will be used for quantitative analyses. Note: this rule not applicable to UACR.

### 2.5.2 Data handling conventions for secondary efficacy variables

Rules defined for the primary efficacy variable will apply to time-to-event of secondary efficacy variables.

### 2.5.3 Missing data

For categorical variables, patients with missing data are not included in calculations of percentages unless otherwise specified. When relevant, the number of patients with missing data is presented.

Derived variables will be considered missing if any of the original variables required to calculate them are missing. For example, if either a baseline assessment or an endpoint assessment is missing for a particular patient, then change from baseline at endpoint will be missing. Depending upon the assessment, analyses may not include all patients in the analysis population, because certain patients in the intended population may have missing data.

#### ***Handling of computation of treatment duration if IMP end of treatment date is missing***

For the calculation of the treatment duration, the date of the last dose of IMP is equal to the date of last administration reported on the end-of-treatment case report form page. If this date is missing or a partial date, the exposure duration should be left as missing.

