#### **2.3.3.1 Extent of investigational medicinal product exposure**

The extent of IMP exposure will be assessed in the safety population by duration of IMP exposure and by category.

Duration of IMP exposure is defined as last dose date – first dose date + 7 day, regardless of unplanned intermittent discontinuations (see [Section 2.5.3](#) calculation in case of missing or incomplete data).

Duration of IMP exposure will be summarized descriptively as a quantitative variable (number, mean, SD, median, minimum, and maximum). In addition, duration of treatment exposure will also be summarized by numbers and percentages for each category and cumulatively. Following are the categories of exposure-range (in months): <3 months, >3 to 6 months, >6 to 12 months, >12 to 18 months, >18 to 24 months, > 24 to 36 months, > 36 months.

Additionally, the cumulative duration of treatment exposure will be provided, defined as the sum of the duration of treatment exposure for all patients, and will be expressed in patient years.

Percentage of injection taken will be summarized, calculated as (total number of planned injections – number of missed injections)/total number of planned injections\*100 during treatment period.

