#### **Severe hypoglycemia**

The severe hypoglycemia will be analyzed on TEAE period.

The following analysis will be provided for severe hypoglycemia:

- Number (%) of patients with at least one severe hypoglycemia
- Number of events per 100 patient-years of total IMP exposure.

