#### ***Handling of adverse events/hypoglycemia when IMP end of treatment date is missing***

For the purpose of defining TEAE period, the date of the last administration of double-blind IMP is equal to the date of the last administration reported on the e-CRF “Treatment Status” page.

If the date of last administration reported on the e-CRF “Treatment Status” page is

- Partially missing, it will be imputed with a date as late as possible before or on the date of death, if the end of treatment reason was death or study discontinuation date if available on the eCRF “Completion of End of Study” or study close-out visit date for patients who completed the study.
- Completely missing, it will be imputed with the date of death, if the end of treatment reason was death or study discontinuation date if available on the eCRF “Completion of End of Study” or study close-out visit date for patients who completed the study.

If the study discontinuation date on eCRF “Completion of End of Study” page is

- Partially missing, it will be imputed with a date as late as possible.
- Completely missing, all adverse events occurred on or after the first administration of double-blind IMP will be considered as treatment emergent adverse events.

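### Severe hypoglycemia events can be counted without their patient-years, because a missing or partial dose date voids exposure but not the treatment-emergent window

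*SAP*

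**What the plan says.** **Denominator.** SAP 2.3.3.1 builds exposure from the dose dates: "Duration of IMP exposure is defined as last dose date" minus first dose date plus 7 days. Cumulative exposure in patient-years is "defined as the sum of the duration of treatment exposure for all patients", and incomplete data are referred to Section 2.5.3. There, the paragraph on computing treatment duration takes the last administration date from the end-of-treatment page and adds: "If this date is missing or a partial date, the exposure duration should be left as missing".

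**Numerator.** The severe hypoglycemia part of SAP 2.3.5.1 states: "The severe hypoglycemia will be analyzed on TEAE period". SAP 2.1.4 ends that window 7 days after the last injection for hypoglycemia. When the last-dose date is unusable, a separate paragraph of 2.5.3 applies, and its heading names hypoglycemia. It begins "For the purpose of defining TEAE period, the date of the last administration of double-blind IMP is equal to" the date on the Treatment Status page, and then imputes:

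- Partial date: "Partially missing, it will be imputed with a date as late as possible before or on the date of death", or up to study discontinuation or the close-out visit, as applicable.
- No date at all: "Completely missing, it will be imputed with the date of death, if the end of treatment reason was death", otherwise the study discontinuation date or the close-out visit date.
- Study discontinuation date also completely missing: every event from first dose onward is treatment-emergent.

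**First-dose date missing.** Another paragraph of 2.5.3 counts events from the day of randomization as treatment-emergent and keeps exposure missing.

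**The rate.** SAP 2.3.5.1 specifies: "Number of events per 100 patient-years of total IMP exposure".

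**The concern.** The rate divides a count that retains participants with unusable dose dates by a person-time total that leaves them out. The exposure rule is also severe for partial dates. Someone treated for two years whose last-dose day is unknown loses the full two years, although the real uncertainty is at most about a month. Severe hypoglycemia is one of the adverse events the protocol singles out for specific monitoring, and this is the one exposure-adjusted rate the SAP defines for it. The cumulative exposure total is understated by the same share.

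**Working it through.** The documents give no hypoglycemia rate or exposure total to reproduce, so the check traces the rules and then sizes the effect.

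**Step 1: one participant through the rules.** Suppose the month and year of the last dose are known, the day is not, and one severe hypoglycemia event occurred during treatment. The adverse-event paragraph of 2.5.3 imputes the latest possible date, so the event counts. The duration paragraph sets exposure to missing, so nothing is added to the sum. The contribution to the rate is 1 event over 0 patient-years. No rule removes the event.

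**Step 2: inflation.** Let E be all events, P the true patient-years and m the share of P set to missing. The reported rate is E / [P(1 - m)], which is the true rate times 1/(1 - m). The documents give no m, so these values are assumed:

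| m | 1/(1 - m) | Inflation |
|---|---|---|
| 1% | 1.010 | 1.0% |
| 2% | 1.020 | 2.0% |
| 5% | 1.053 | 5.3% |

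**Step 3: a benchmark from the SAP's planning assumptions.** SAP 1.3 assumes about 4000 participants, 2% annual early study discontinuation and 24 to 36 months of follow-up. Assume further uniform accrual, exponential discontinuation and treatment until a participant leaves the study. Then μ = -ln(0.98) = 0.0202 per year, with potential follow-up T uniform on 2 to 3 years.

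- Mean exposure: average of (1 - e^(-μT))/μ = 2.437 years, so 4000 × 2.437 ≈ 9,750 patient-years.
- Share leaving early: average of 1 - e^(-μT) = 4.9%.
- Share of patient-years held by early leavers: average of [(1 - e^(-μT))/μ - T e^(-μT)], divided by 2.437, = 2.5%.
- If every early leaver lacked a usable date: 1/(1 - 0.0254) = 1.026, an inflation of about 2.6%.

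This is a benchmark, not a ceiling. Participants who stop IMP but stay in the study could also lack a date, and the documents assume no rate of treatment discontinuation.

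**Step 4: the same case with the partial date imputed.** With only the day unknown, the error is at most about 30 days. Against an average exposure of 2.437 × 365.25 ≈ 890 days, that is 30/890 = 3.4% of one participant's exposure, instead of 100%. With only the year known, the error can reach about 12 months.

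**Step 5: comparison between arms.** The active-to-placebo rate ratio is multiplied by (1 - m_placebo)/(1 - m_active). As a hypothetical, a 5% loss on active and 2% on placebo gives 0.98/0.95 = 1.032; reversed, 0.95/0.98 = 0.969. Equal losses cancel.

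**The case against.** The best defence is that the split is deliberate. The adverse-event paragraph limits its imputation to defining the treatment-emergent period, and SAP 2.3.5.1 intends adverse-event classification to be conservative. SAP 2.5.3 treats a derived variable as missing when a source variable is missing. When in doubt, then, the plan counts the event and does not credit unverified exposure, which overstates the rate of a harm. That stands as a reason not to invent exposure. It does not justify a rate whose two parts cover different participants, and an upward error in each arm is not conservative for a comparison when the losses differ.

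Two further points carry weight. Protocol 6.4, 7.1 and 7.1.1 require compliance tracking and documented IMP discontinuation, so unusable dates may be rare. Safety analyses are descriptive, and the duration summary shows the number of participants with data, so a shortfall would be visible.

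The general remark in SAP 2.5.3 that some analyses may not include all patients could be read as dropping these participants from the rate. No rule does so for this count, and the adverse-event paragraph exists to classify their events.

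A reader might infer that the affected participants are mainly those lost or withdrawn, and that arms will therefore differ. The documents show neither; the imputation rules also provide for deaths and study completers. A reader might also infer that the imputed date can be reused for exposure in every case at no cost. It cannot. Protocol 4.1 and 7.1.1 keep participants in follow-up after they stop IMP, so a completely missing date imputed as close-out could credit long off-drug time as exposure and dilute the rate. If the study discontinuation date is completely missing as well, the SAP supplies no date to reuse.

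**Conclusion.** The mismatch follows from the SAP's own rules: severe hypoglycemia events can be counted without the corresponding person-time, and the rate per 100 patient-years is then biased upward by 1/(1 - m). The size is uncertain, because m is assumed throughout. The inflation is about 1.0% to 5.3% for m of 1% to 5%, and about 2.6% in the early-leaver benchmark with its stated assumptions. A single participant with 36 months of lost exposure is 3/9,750, or about 0.03%, of the planned total.

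The consequence is limited to the descriptive event rate and the exposure summaries. The number (%) of patients with severe hypoglycemia, the MACE analyses and the testing hierarchy are untouched. Who would be affected, and whether the arms would differ, cannot be told from the documents. This is a minor correction worth making because it is cheap.

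**What to change.** Amend SAP 2.5.3 as follows:

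1. **Partial last-dose date:** use the date imputed for the treatment-emergent window for exposure duration and patient-years as well.
2. **Only the first-dose date missing:** start exposure at the randomization date, which that paragraph already uses to classify events.
3. **Completely missing last-dose date:** do not credit exposure to close-out by default. Compute the severe hypoglycemia rate with these participants removed from both numerator and denominator. Latest-date imputation can be an optional sensitivity analysis where a date is available.
4. **Reporting:** give the number of imputed and excluded cases by arm, and use one name for the case report form page that supplies the last-dose date.

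The cost is a few sentences and a small amount of extra analysis. Exposure may be overstated by up to about one month per participant when only the day is unknown, and by up to about 12 months when only the year is known.
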